## Changes to the Original Study Protocol

### Research Plan Changes:

#### 1. January 12, 2018

- a. Increased the number of Drayer Physical Therapy clinic sites from 24 to 25 due to Drayer's purchase of the Fulton, MS clinic.

#### 2. May 16, 2019

- a. Four Upstream Rehabilitation Inc. sites (Wiggins, Smyrna, Prattville and Saltillo) were replaced with four sites due to contamination issues, site not opening, and low recruitment opportunities. The replaced sites included two new sites (Forest, MS and Bristol, TN) under Upstream Rehabilitation Inc. and two sites (Phenix City, AL and Grenada, MS) under Encore Physical Therapy.

- b. Five new sites were added, with two as study sites and three as satellite sites.

The two newly added study sites were Ruleville, MS under North Sunflower Medical Center and Greenville, MS under River City Rehabilitation. These two sites were added to serve the Delta area of Mississippi. The three newly added satellite sites were Ashland City, TN and Cookeville, TN under Upstream Rehabilitation Inc. and Mobile, AL under Encore Physical Therapy. Satellite sites were added to help with recruitment and testing needs. Therefore, the number of participating clinic sites increased to 43, with three of the sites serving as satellite sites.

#### 3. March 24, 2020

- a. Our stakeholder panel and the research team determined that *meeting physical activity guidelines* should be added to the inclusion/exclusion criteria to ensure that the intervention being delivered was the catalyst for change and not another exercise routine. Therefore, the *Godin Leisure Time Exercise Questionnaire (GLTEQ)* was added to the exclusion criteria and a GLTEQ score  $\geq 24$  was used as an indicator of individuals meeting physical activity guidelines during the screening process. This addition was approved by our IRB on July 25, 2017.
- b. The EDSS (1-7) was changed to PDDS (0-7) as an inclusion criterion. The rationale for this change was discussed with our stakeholder panel and research team upon realization that very few people with MS knew their EDSS score. This change was approved by our IRB on July 25, 2017.
- c. To honor our commitment to participants enrolled in the study and provide them with the intervention and follow-up assessments remotely during Covid-19, we requested approval for the following modifications:
  - i. Contacted all therapists and participants to suspend onsite visits and requested their participation in completing the intervention (rDirectCAM) and/or performing all testing remotely (teleassessment).
  - ii. The following steps were followed for offering rDirectCAM to participants:
    - For those enrolled in DirectCAM who had started the Intervention (n=25):

- Sent participants a tablet with access to a Zoom link for rDirectCAM.
- Trained therapists to deliver rDirectCAM remotely through the Zoom platform.
- For participants who did not have internet access, we offered a phone call option in which the therapist went through the exercises with the participants via phone, utilized the provided DirectCAM booklet (e.g., “Ok. Now turn to page 3 and let’s do the Warrior pose.”)

4. August 20, 2022

- a. The Covid-19 Enhancement study was added into the research plan.

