**TeleCAM.** The TeleCAM participants received the same intervention content as DirectCAM. The only difference was that the TeleCAM participants received the intervention via exercise videos preloaded to a tablet that was given to them upon enrolling in the study. The exercise videos were filmed with a person with MS instructing and demonstrating the CAM program. Each TeleCAM participant began with one onsite training session with a study therapist. In the training session, participants were shown how to turn the tablet on and off to watch the videos, perform the basic exercises correctly, and use the yoga and Pilates equipment. Participants were asked to bring a family member or friend with them in case they needed assistance using the tablet. The TeleCAM participants were contacted by an Interactive Voice Response (IVR) system-initiated call at their preferred dates and times (aligned with the general intervention timeline) to promote adherence to the yoga/Pilates exercise and neurorehabilitation practice. The IVR system is an automated communication system that includes computers, specialized phone hardware, and operating software to allow immediate computer-assisted interaction with participants by telephone. It was developed during our research team's past physical activity research and in the current study was adapted to address the specific concerns of individuals with MS (physical activity progress, pain, fatigue, and key motivational variables from the SCT). The IVR calls were sent to only

TeleCAM participants weekly for the first six months, and then biweekly for months 6-12 to monitor physical activity, pain, fatigue, and quality of life for SCT variables.

**rDirectCAM.** The rDirectCAM was developed in response to the Covid-19 pandemic and was the Enhancement study intervention. Participants enrolled in rDirectCAM received the same intervention as DirectCAM. The only difference was that the rDirectCAM participants utilized a remote platform at home to work synchronously with a therapist.

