## Analytical and Statistical Approaches

### **Main Study**

Our analysis was following ITT protocol as all participants assigned to the randomized clinics and completed baseline assessment were included in the analysis.

Our primary hypotheses were about comparing the change in the 11 outcomes (listed in **Table 4**) between baseline and 12th month follow-up across the two arms. We considered these 11 hypothesis tests for the 11 outcome variables as part of a single family of hypotheses. We employed the Holm-Bonferroni method for controlling the overall family wise error rate and computed adjusted *p*-values. For each outcome we used a linear mixed effects model, with TeleCAM arm as the reference category, and accounting for the correlated nature of the data due to the nesting of participants within a clinic as random effects. Crude models included fixed effects included both Arms (TeleCAM, DirectCAM), Time (baseline [reference], 3 month, 6 month, 12 month), an Arms X Time interaction, and accounted for randomization strata (clinic location being urban vs. non-urban). The interaction of Arms and Time variables was the primary effect of interest since it quantified the differences within Arm change in the outcome from baseline over time of the two Arms. For example, based on the fitted model that included the interaction between Arm and Time, the difference in change over time from baseline to 12 months between DirectCAM and TeleCAM were estimated. Contrast statements were used to test the null hypotheses in conjunction with the fitted model coefficients and standardized differences in the average treatment effect reported. The estimates of the change in health and function outcomes for each arm and their 95% confidence interval were also reported. As a sensitivity analysis, similar models additionally adjusted for sex, race, and post-COVID data collection measure indicated were also ran. Note that, since post-COVID, data collection for patient reported outcomes was conducted remotely for remaining participants, the former was also included as a covariate in the adjusted model. Next, missingness in primary and secondary outcomes were addressed using multiple imputation technique (MCMC) via PROC MI in SAS,

assuming missing at random. Additional sensitivity analyses were conducted using wild bootstrap to assess the robustness to model assumptions.

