### **Enhancement Study**

We used a quasi-experimental design to compare rDirectCAM with DirectCAM. Our hypothesis posits that the observed difference in outcome effects between rDirectCAM and DirectCAM is less than a predetermined non-inferiority margin ( $-\Delta$ ). These margins were selected based on the MCID or minimal detectable change (MCD) of the studied outcomes among MS population published in literature (MFIS= 4, BBS= 3, TUG= 10.6, FTSTS= 13, Grip-strength= 10.5, SF-36 Physical functioning= 7.1 and SF-36 pain= 4.9).

Specifically, we hypothesized that the effect of rDirectCAM was not inferior to that of DirectCAM by a margin that was considered clinically acceptable, thereby affirming the non-inferiority of rDirectCAM in comparison to DirectCAM. In other words, if the resulting *p*-value was significant, this would mean that we rejected the null hypothesis which stated that the difference in the effect between two arms were more than the non-inferiority margin. Statistical significance level of 0.05 and at confidence interval 95%, same as superiority trials,

was applied to determine non-inferiority. To achieve a balance between the study arms, several analyses involved regression-based parametric adjustment measures that are sensitive to model misspecification. Propensity scores are another widely used measure to achieve balance or matching between the study arms. These scores model the probability of being assigned to the given treatment conditional on observed baseline covariates obtained via measures including matching, inverse probability treatment weighting (IPTW), and stratification and covariate adjustment. Matching-based measures such as nearest neighbor matching algorithm often led to study participants being excluded when a match was not available. This may have potentially biased the effect estimates. When this occurred, we utilized stabilized IPTW, a non-parametric balancing strategy, to achieve balance between the two study arms (rDirectCAM and DirectCAM). Using this weighted analysis, we modeled the causal parameter as the inverse of the conditional probability of receiving the treatment given the observed covariates, a technique that provides asymptotically unbiased estimates and uses data on all available study participants across the two arms.

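### Up to 25 DirectCAM participants were offered rDirectCAM mid-programme, and the Enhancement analysis does not say how they are handled; any who accepted dilute the non-inferiority contrast.

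*Combined protocol and SAP*

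**What the plan says.** The Enhancement Study part of the analysis section states the contrast: "We used a quasi-experimental design to compare rDirectCAM with DirectCAM". It is tested for non-inferiority, with a margin of 4 points for MFIS. The rDirectCAM paragraph under Interventions says it has the same content as DirectCAM and adds: "The only difference was that the rDirectCAM participants utilized a remote platform at home to work synchronously with a therapist".

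Item 3c of the Research Plan Changes, dated March 24, 2020, records the suspension of onsite visits and the steps followed for one group: "For those enrolled in DirectCAM who had started the Intervention (n=25"). The steps were "Sent participants a tablet with access to a Zoom link for rDirectCAM" and "Trained therapists to deliver rDirectCAM remotely through the Zoom platform". It continues: "For participants who did not have internet access, we offered a phone call option".

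On who is analysed, the Main Study text says "all participants assigned to the randomized clinics and completed baseline assessment were included in the analysis". The Enhancement text says that the weighted analysis "uses data on all available study participants across the two arms". Neither mentions participants whose mode of delivery changed.

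**The concern.** In a superiority comparison, keeping people in their assigned arm after a change of treatment usually works against the claim. In a non-inferiority comparison it works for the claim. If rDirectCAM is truly worse, DirectCAM participants who received it bring the two group means closer together, and a deficit at or beyond the margin is more likely to pass. If the two modes are truly equal, there is no bias.

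At stake is the error rate of the Enhancement study's central conclusion, that remote synchronous delivery is not materially worse than on-site delivery. A reader cannot tell from the documents how much of the on-site comparator was actually treated on site.

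**Working it through.** **1. Are the 25 already the rDirectCAM arm?** No. Time Frame for the Study says that arm came from interested people who could not enrol before the Main study stopped. The 25 were already enrolled in DirectCAM.

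**2. Does anything remove or adjust for them?** The Enhancement text has no exclusion, censoring, reclassification or on-site-only set. Its sensitivity analyses concern distributional and modelling assumptions. The post-COVID covariate belongs to the Main-study adjusted model and is justified by remote data collection, not by mode of delivery. Table 5 still shows DirectCAM sessions as on-site only.

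**3. Planned sizes** (Sample Size Calculations and Study Power).
- rDirectCAM: 55/(1 - 0.25) = 73.3, rounded up to 74, as stated.
- Main study: 533/(1 - 0.35) = 820, as stated.
- The 55 cannot be reproduced, because neither an MFIS SD nor a comparator size is given.

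**4. Inputs.** Margin 4; 80% power; one-sided 0.05. The analysis section refers to a 95% confidence interval; if that is two-sided, the one-sided level is 0.025, so both levels are shown. Assumption: equal Main-study arms, so DirectCAM has 820/2 = 410 enrolled or 533/2 = 266.5 completers.

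**5. Formulas.** Let f be the share of the comparator effectively treated remotely.
- Observed difference = true difference x (1 - f).
- Standard error implied by the design: 4/(1.645 + 0.842) = 1.609 at one-sided 0.05; 4/(1.960 + 0.842) = 1.428 at 0.025.
- Type I error at the margin = Φ(-z + 4f/SE).

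**6. All 25 retained and fully remote.**
- f = 25/410 = 6.1%, or 25/266.5 = 9.4%.
- A true deficit of 4 is seen as 3.76 or 3.63.
- One-sided 0.05: Φ(-1.645 + 0.244/1.609) = 6.8%; Φ(-1.645 + 0.375/1.609) = 7.9%.
- One-sided 0.025: Φ(-1.960 + 0.244/1.428) = 3.7%; Φ(-1.960 + 0.375/1.428) = 4.5%.

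The 9.4% sets people who had started against planned completers. If the 25 also drop out at 35%, 25 x 0.65 = 16.25, and 16.25/266.5 = 6.1%.

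**7. Partial exposure** (one-sided 0.05).

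| Share of programme remote | f | Type I error |
|---|---|---|
| All | 6.1-9.4% | 6.8-7.9% |
| Half | 3.0-4.7% | 5.8-6.3% |
| One fifth (4 of 20 sessions) | 1.2-1.9% | 5.3-5.5% |

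**8. Smaller comparator, for illustration only.** The Enhancement text mentions matching. If matching left 74 comparators and all 25 were among them, fully remote, f = 25/74 = 34% and type I error would be 21%.

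**The case against.** The strongest reply is that item 3c records an offer. A reader might infer that 25 people were switched and that the comparator therefore contains the test intervention. The documents do not establish this: uptake is not given and could be zero, and telephone sessions are a third mode, neither on-site DirectCAM nor video-based rDirectCAM. Inclusion in the comparator is itself inferred from the wording about all available participants and the absence of an exclusion. All of this stands, and it is why the point concerns unstated handling.

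Exposure was also mixed, since everyone in the group had begun the intervention. Enrolment is said to have ended in 2019, and twelve weeks from December 31, 2019 is March 24, 2020, so prompt starters would have been near the end, in the weekly phase of 4 of 20 sessions. That supports the lower rows of the table. It does not settle the matter: start delays are unknown, and the same section speaks of people prevented from enrolling when the pandemic stopped the Main study.

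Finally, dropping only those who accepted remote delivery would select on behaviour after baseline in a comparison that is already non-randomised. That is a fair criticism of such an exclusion. A cut at the study-wide suspension date, applied to everyone still in the intervention, avoids it because the date does not depend on individual response.

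**Conclusion.** The concern holds as a gap in the plan with a known direction. Up to 25 participants assigned to DirectCAM may have received the test mode of delivery, the non-inferiority analysis does not address them, and any effect favours the claim when rDirectCAM is truly worse.

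At planned size the effect is modest. A true MFIS deficit of 4 loses 0.24-0.38 points if all 25 were retained and fully remote, and less with partial exposure. The calculation assumes equal planned arms, the precision implied by 80% power, and telephone delivery counted as remote.

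A reader might take the 6.8-7.9% as an upper bound. It is one only for uptake and exposure at the planned arm sizes. The actual DirectCAM size is not in the documents, and a smaller or matched comparator would give a larger dilution. The figures show a range under stated assumptions and do not estimate what happened.

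**What to change.** 1. Report how many of the 25 accepted remote delivery, by Zoom or by telephone, and after how many on-site sessions.
2. In the Enhancement non-inferiority analysis, censor the data of all DirectCAM participants still in the intervention at the date onsite visits were suspended, whether or not they accepted. Alternatively, restrict the comparator to those who completed on site before that date. Table 5 places the first post-baseline assessment at the end of month 3, so those censored would contribute little beyond baseline. The plan should say whether multiple imputation is applied to their censored values.
3. Show the all-participants analysis alongside, and claim non-inferiority only if both agree.
4. Keep these participants as assigned in the Main intention-to-treat analysis.

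The cost is a date flag, some SAP wording and at most about 6-9% of comparators at planned size. Precision barely changes because rDirectCAM is the small arm. With 55 rDirectCAM completers and equal variances, the SE ratio is √[(1/55 + 1/242)/(1/55 + 1/267)] = 1.009 if 267 comparators fall to 242, and √[(1/55 + 1/385)/(1/55 + 1/410)] = 1.004 if 410 fall to 385. Requiring agreement makes the claim somewhat harder to reach.

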**Research Analysis Changes:**

The seven SF-36 subscales were studied as exploratory outcomes. This was done because they captured all aspects of QOL, and we were interested to explore what was the effect of intervention on each domain.
